6	0.38	0.21	0.58
8	0.50	0.31	0.69
10	0.62	0.42	0.79
12	0.75	0.55	0.88
14	0.88	0.68	0.96

Therefore, with a sample size of 16 subjects, the 90% confidence interval for the two-year survival/two-year recurrent-free survival rate will be no wider than 38%.

Secondary endpoints of this pilot study include adverse events, immunological parameters, density & phenotype of cellular infiltrate and expression of GD2 target antigen, and IFN- γ expression. Assuming a total sample size of 16, the probability of observing at least one incidence of Grade ≥ 3 toxicity is 81%, if the true toxicity rate is 10%. Analogously, the probability of observing at least one incidence of Grade ≥ 3 toxicity is 93%, if the true toxicity rate is 15%. Immunological parameters will be measured on a continuous scale. Assuming a sample size of eight subjects per

study arm, a difference of 1.5 standard deviation units in magnitude will be detected with 80% power at a two-sided significance level of 0.05 (based on a two-sample t-test). A difference of only 1.25 standard deviation units will be detected with 63%. Smaller differences are unlikely to be detected as statistically significant.

In order to account for “unevaluable” subjects and drop-outs (e.g., patients without an evaluation following course 2 of IC treatment), we will accrue up to 20 eligible subjects (10 per arm) in total. Based on our past experience with advance melanoma subjects treated at UWCCC, we expect to accrue 20 eligible subjects within 24 months. The minimum follow-up period will be 12 months after the last subject has entered the study.

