9.4.5 Secondary Endpoints

The number and severity of toxicity incidents will be analyzed descriptively in tabular format. Immunological parameters, i.e., lymphocyte counts, NK/ADCC, soluble IL2, anti-idiotypic antibodies, and anti Fc-IL2, will be summarized by standard descriptive statistics in terms of means, standard deviations, medians and ranges for each measurement time point (see Section 7.3) and group separately. Within each group, differences between pre-IC treatment values and post-IC treatment values will be evaluated by paired t-tests and/or non-parametric Wilcoxon test.

Comparisons of immunological parameters between the two study arms will be performed by two-sample t-tests. Furthermore, longitudinal data analyses of immunological parameters will be performed to incorporate the time effect. Specifically, linear and/or nonlinear mixed effect models with subject specific random effects and generalized estimating equations (GEE) models with identity link and exchangeable (working) correlation structures will be used to account for the correlation between repeated measurements of immunological parameters. Missing data may be imputed using regression type imputation techniques. For immunological parameters not conforming to the assumptions of parametric analysis, the non-parametric Wilcoxon Rank Sum test will be used for comparing the two study arms. The association between the various immunological parameters will be examined by computing Spearman's rank correlation coefficients and linear or nonlinear regression techniques. Immunological parameters will be correlated with clinical endpoints by fitting Cox regression models (for clinical endpoints overall survival & time to recurrence) and logistic regression analysis models (for clinical endpoints toxicity and histological evidence of anti-tumor activity). The data of all immunological parameters will be presented graphically where possible (boxplots, histograms, profile plots and scatterplots).

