The analysis of GD2 target antigen expression, density and phenotype of cellular infiltrate, vascularity, IC binding, and IFN- γ expression will be exploratory by necessity. Expression levels for these will be summarized in terms of means, medians, standard deviations and ranges where possible. Comparisons of expression levels between the two groups will be performed using two-sample t-tests (after appropriate transformations) and/or non-parametric Wilcoxon Rank Sum tests. Phenotypes of cellular infiltrate will be summarized in tabular format. Differences of phenotype frequencies between the two groups will be evaluated using Fisher's exact tests.

Augmentation of T cell reactivity to autologous tumor or to known melanoma antigens will be analyzed descriptively. The level of significance of each hypothesis test involving secondary endpoints will be 0.05. Due to the exploratory nature of these analyses, there will be no multiplicity adjustment.

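### Section 9.4.5 permits regression imputation of missing immunology values without limiting its use or carrying its uncertainty into the tests; if single imputation is used, the 5% level can be exceeded at 8 per arm

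*Combined protocol and SAP*

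**What the plan says.** Section 9.4.5 of the combined protocol and SAP sets out several analyses of the immunological parameters. Within each group, "differences between pre-IC treatment values and post-IC treatment values will be evaluated by paired t-tests" and/or a Wilcoxon test. Between arms it plans two-sample t-tests, or the rank sum test where parametric assumptions fail. For the repeated measurements it adds: "Specifically, linear and/or nonlinear mixed effect models with subject specific random effects", together with GEE using an exchangeable working correlation.

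Directly after the mixed-model and GEE sentence comes the only missing-data rule for these parameters: "Missing data may be imputed using regression type imputation techniques". The text then returns to comparing the two arms.

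On the error level: "The level of significance of each hypothesis test involving secondary endpoints will be 0.05". The section calls these analyses exploratory and makes no multiplicity adjustment. Section 9.3.2 sizes the between-arm t-test on 8 subjects per arm: "a difference of 1.5 standard deviation units in magnitude will be detected with 80% power at a two-sided significance level of 0.05". It also states "we will accrue up to 20 eligible subjects (10 per arm) in total" to allow for unevaluable subjects.

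**The concern.** Single regression imputation replaces a missing value by a prediction from the observed ones and then treats it as a measurement. The filled values add no information, yet they raise the apparent sample size and, when they lie on the fitted line, reduce the spread. The standard error comes out too small and the test rejects too often. With 8 per arm, two or three filled values are a quarter or more of the data.

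In vivo immune activation is secondary objective 2.2.2, and the within-group pre/post test is the analysis that speaks to it most directly. Standard errors that are too small would produce apparent activation where there is none.

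Some gaps can be foreseen. NK/ADCC and the pilot T-cell assays are done on selected patients (Sections 7.3.4 and 7.3.6), and Course 3 is given only to subjects in complete response after Course 2 (Section 5.3.1.2).

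**Working it through.** **Inputs from the documents.** 8 per arm and two-sided 0.05 (Section 9.3.2); 0.05 per secondary test, with paired and two-sample t-tests, mixed model and GEE (Section 9.4.5). **Assumptions, not in the documents.** 1, 2 or 3 of 8 post-treatment values missing completely at random in each arm; pre/post correlation 0, 0.5 or 0.8; normal data.

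**1. The plan's own power.** For a two-sample t-test the noncentrality is d·√(n/2), here d·√4 = 2d, with 14 df and critical value 2.145.
- d = 1.5: noncentrality 3.0, power 79.7% (plan: 80%).
- d = 1.25: noncentrality 2.5, power 64.3% (plan: 63%).

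The plan's figures therefore belong to the two-sided t-test at a true 5% level with 8 real values per arm.

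**2. A hand check of the mechanism.** Take zero correlation and arm in the imputation model, so that each missing value is filled, in effect, with its arm mean. With m of 8 observed:
- True variance of an arm mean: σ²/m.
- Expected variance used by the test: σ²·[(m−1)/7]/8.
- Ratio: [(m−1)/7]·(m/8).

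For m = 6 the ratio is (5/7)(6/8) = 0.536. The test rejects when the correct statistic, which has 10 df, exceeds 2.145·√0.536 = 1.570. That has two-sided probability 14.8%. For m = 7 the ratio is 0.750 and the error 8.8%; for m = 5, 0.357 and 23.6%.

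**3. Simulation under no effect** (10,000 trials per setting; simulation error √(0.05·0.95/10,000) = 0.2 points). Post values are predicted from baseline. Ranges run over the three correlations; entries are percent rejections at nominal 5%.

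| Handling | Test | 1/8 missing | 2/8 missing | 3/8 missing |
|---|---|---|---|---|
| Observed values only | two-sample | 4.9 | 4.9-5.2 | 4.9-5.1 |
| | paired | 4.7-5.2 | 4.9-5.1 | 4.6-4.9 |
| Predicted value, arm in model or fitted per arm | two-sample | 6.6-8.5 | 8.1-14.2 | 11.3-22.3 |
| | paired | 6.5-8.1 | 9.4-13.2 | 13.1-20.6 |
| Same with arm in model, plus one random residual | two-sample | 6.0-8.1 | 8.2-11.7 | 9.9-17.2 |
| | paired | 6.4-7.6 | 8.5-10.9 | 11.3-14.6 |
| Predicted value, arms pooled | two-sample | 4.9-5.2 | 4.7-5.2 | 4.8-5.4 |
| | paired | 6.2-6.9 | 7.2-8.9 | 9.0-13.3 |
| Same, plus one random residual | two-sample | 4.8-5.3 | 5.0-5.1 | 5.2-5.6 |
| | paired | 5.7-6.1 | 6.7-7.7 | 7.8-9.9 |

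At zero correlation with arm in the model, the simulated two-sample errors are 8.5%, 14.2% and 22.3%, close to the hand check. With 2/8 missing and arm in the model or fitted per arm, the test's variance is 55-81% of the true variance. The paired test is inflated in every imputed row. The two-sample test is inflated only when arm is in the model.

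**4. The longitudinal methods on observed data** (600 trials, simulation error √(0.05·0.95/600) = 0.9 points; 4 visits, intraclass correlation 0.5, 2/8 missing at the last visit in each arm). The random-intercept mixed model gives 6.3% with a normal reference and 3.2% with t on 14 df. GEE with robust standard errors and a normal reference gives 10.7%. So dropping imputation is not enough: at this size the longitudinal methods need a small-sample correction of their own.

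**The case against.** A reader might infer that the plan prescribes single imputation followed by t-tests. It does not. The wording is optional, and the phrase covers multiple imputation by regression, whose combined variances are designed to carry the missing uncertainty. Nothing says the filled values feed the t-tests, and the sentence follows the mixed-model and GEE sentence, so it may have been meant for those alone. All of this stands: the inflation is a risk left open. But the sentence is not confined to any analysis, and multiple imputation is not mentioned. The plan's other missing-data rule, in Section 9.4.2, is itself a single-value substitution (the screening value for a missing pre-treatment value). An analyst could follow the text and choose an invalid route.

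A reader might also infer that both t-tests are necessarily inflated. The two-sample test holds its level when the imputation model leaves arm out.

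Nor does the mixed model make every missing-data provision unnecessary. It is valid on observed values under missing at random, but the GEE planned beside it generally needs missing completely at random unless weighted or imputed. Simply deleting the sentence would leave that unaddressed.

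The amount of missingness is uncertain. Subjects not in complete response after Course 2 are replaced (Section 5.3.1.3), and entry continues until 8 per arm have had surgery and two courses (Section 5.1). This reduces the Course 3 gap without removing it, since toxicity or refusal can also end treatment (Section 5.5.1). The serum assays (soluble IL2 receptor, anti-hu14.18-IL2 antibody) have no selected-patient restriction, and T-cell reactivity is only described.

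Finally, Section 9.4.1 makes the analysis mainly descriptive. Exploratory status does excuse the lack of multiplicity adjustment; it does not excuse a standard error that is too small.

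**Conclusion.** The concern holds as a conditional one. The plan leaves open a form of imputation that would break its own 0.05 level. If singly imputed values enter the tests, with 2 of 8 missing at random per arm, the paired error is about 7-13% and the two-sample error about 8-14% with arm in the imputation model, or about 5% without it. Observed-data t-tests hold about 5%. These sizes rest on assumed missing rates, correlations and normal data. They do not describe selection by response or by assay, where the gaps may not be random.

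The reach is limited. The sentence stands under the secondary endpoints, and the documents do not support extending it to the primary histology comparison, time to recurrence, overall survival or the toxicity stopping rule. It is still worth correcting, because it bears on a stated objective and Section 1.5.3 foresees that the results could lead to a larger trial.

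**What to change.** Replace the imputation sentence in Section 9.4.5 with text to this effect:
- The main longitudinal analysis is the mixed model fitted to observed values, with a small-sample degrees-of-freedom correction.
- Paired tests use observed pairs, and two-sample and Wilcoxon tests use observed values; the number analysed is reported for each.
- GEE is supportive, with a small-sample variance correction and its missing-completely-at-random assumption stated.
- Imputation, if used, is multiple imputation with combined variances, as a sensitivity analysis only, with the predictors named.
- Values uncollected by design (selected-patient assays, Course 3 not given) are not imputed.

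This changes SAP wording only; no sample, visit or assay is added. The price is fewer subjects in the t-tests and somewhat wider intervals. Section 9.3.2's power applies to 8 observed values per arm, so it will be lower for any parameter with gaps. Observed-data tests hold their level here under random missingness; if missingness depends on outcome, no option listed removes the bias, and the report should say so.

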9.4.9 Stopping rules for excessive toxicity

Many of the dose limiting toxicities (DLTs) that occur due to hu14.18-IL2 therapy are not unexpected. However, a subset of the DLTs described in Section 5.0 of the protocol are considered unacceptable. Those DLTs are:

1. Toxicity requiring the use of vasopressors, including Grade 4 vascular leak syndrome and/or grade 4 hypotension, and
2. Toxicity requiring ventilatory support, including Grade 4 respiratory toxicity.

If at any time a patient requires ventilatory support, new accrual to the study will be temporarily stopped, and the study will be reviewed for safety, dose modification and safety modification.

[figure not shown]
Based on this, a decision regarding reopening the study, likely with an appropriate amendment, would be made by the DSMC, working with the study committee.

Furthermore, accrual to this study will be temporarily suspended at any stage during the accrual period if an excessive toxicity rate is observed. An excessive toxicity rate is defined as follows:

1. At least 15% for Grade 4 vascular leak syndrome or grade 4 hypotension toxicities, or
2. At least 33% for any Grade 4 DLTs.

Evidence that the toxicity rate is excessive will be considered sufficient if the lower limits of the 90% one-sided confidence intervals for the estimates of the true toxicity rates exceed the toxicity limits defined above (i.e., 15% for Grade 4 vascular leak syndrome or hypotension, 33% for any grade 4 DLTs).

Operationally, this will occur if any of the following events occur: Grade 4 vascular leak syndrome or Grade 4 hypotension toxicities are present in at least 2 out of 3 (or less) patients, 3/7, 4/12, 5/17, or 6/20 of the patients accrued, or if any Grade 4 DLTs are present in at least 3 out of 3, 4/6, 5/8, 6/10, 7/13, 8/15, 9/17, or 10/20 of the patients accrued. If one of these thresholds is reached, accrual will be temporarily suspended and the study will be reviewed for safety, dose modification and safety modification. The study would only be reopened if modifications can be made, and approved by the DSMC and the UW-IRB, to assure that patient safety is reestablished. If not, the study would be closed. The stopping rule is illustrated in the following figure:

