5.4 Dose limiting toxicity and subsequent courses at reduced dose

5.4.1 Definition of DLT

The definition of DLT in this study differs from the standard definition. Dose-limiting toxicity (DLT) will be defined as Grade 3 or 4 toxicity, using the NCI Common Terminology Criteria for Adverse Events (CTCAE), version 3.0, EXCEPT as detailed below in Section 5.4.3. These toxicities will be evaluated for all subjects beginning on Course 1 day 1 during all courses of this study except for the time from the initiation of the surgical resection until recovery from surgery and initiation of Course 1 (for Group B) or Course 2 (for Group A) of protocol treatment.

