10.2.3.2.2 Hypotension

Mild hypotension with systolic blood pressure 10-15% below baseline is common in patents receiving IL2.

- a. Asymptomatic patients with mild hypotension should be monitored closely
- b. Symptomatic patients or those with systolic blood pressure < 85 mmHg or < 100 mmHg if representing a decrease in systolic blood pressure $> 20\%$ from the lowest value of any documented systolic blood pressure obtained since study consent was signed should be treated for hypotension. (Do not include blood pressures obtained on days of hu14.18-IL2 treatment after hu14.18-IL2 infusion started for purposes of getting this lowest usual blood pressure).

Patients meeting the above guidelines should be given a 500 ml IV bolus of normal saline over 15 minutes. If unresponsive:

- Stop the hu14.18-IL2 infusion
- Repeat the fluid bolus: 500 ml IV bolus of normal saline over 15 minutes. Fluid bolus may be repeated once or twice as needed. May be limited by symptomatic fluid overload (i.e. pulmonary edema, tense ascites).
- If unresponsive to fluid bolus, may give Albumin (25%) 50 gm IV, then q 6-12 h PRN if serum albumin ≤ 3.0 .
- RBC Transfusion to maintain Hgb ≥ 10.0 g/dL
- If responsive, (i.e., blood pressure increases to a systolic blood pressure over 100 mm Hg or to the patient's blood pressure prior to administration of hu14.18-IL2 for that day if the baseline systolic blood pressure was less than 100 mm Hg), may reinitiate the hu14.18-IL2 treatment on the following day (if scheduled) at

50% reduced dose. If hypotension is recurrent, treatment will be stopped and patients managed as outlined above in this section. Treatment can be restarted (at their next scheduled infusion day) at 25% of the initial dose, if systolic blood pressure is responsive to the fluid management described above. If hypotension is recurrent at this 25% dose, treatment will be discontinued and the patient will be off protocol therapy.

c. Symptomatic hypotension that does not respond to these measures requires:

- IV vasopressors, (i.e., phenylephrine, dopamine, etc.)

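### Section 9.4.9 calls DLTs requiring vasopressors unacceptable, but its accrual-suspension counts name only Grade 4 events, so a vasopressor-treated DLT graded 3 would enter no count

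*Combined protocol and SAP*

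**What the plan says.** Section 9.4.9 states that "a subset of the DLTs described in Section 5.0 of the protocol are considered unacceptable" and lists two kinds. Item 1 is "Toxicity requiring the use of vasopressors, including Grade 4 vascular leak syndrome and/or grade 4 hypotension". Item 2 is toxicity needing ventilatory support, with Grade 4 respiratory toxicity as its included example.

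The two items are then handled differently.

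- **Ventilatory support** has its own trigger, tied to the intervention and not to a grade: "If at any time a patient requires ventilatory support, new accrual to the study will be temporarily stopped".
- **Vasopressor use** has no such trigger. The first excess-rate limit reads "At least 15% for Grade 4 vascular leak syndrome or grade 4 hypotension toxicities". The second is 33% for any Grade 4 DLT. The confidence-limit sentence repeats both ("15% for Grade 4 vascular leak syndrome or hypotension, 33% for any grade 4 DLTs"). The operational rule starts to apply when "Grade 4 vascular leak syndrome or Grade 4 hypotension toxicities are present in at least 2 out of 3 (or less) patients" and continues with 3/7, 4/12, 5/17 and 6/20.

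In Section 5.4.1, "Dose-limiting toxicity (DLT) will be defined as Grade 3 or 4 toxicity", apart from the exceptions in 5.4.3. Neither hypotension nor vascular leak is among those exceptions. The period from the start of surgery until treatment begins again is excluded from DLT evaluation.

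**The concern.** Item 1 defines the unacceptable class by what the patient needed. The two Grade 4 events are introduced as members of that class, not as its limits. The counts keep the two examples and drop the class. A DLT that needed vasopressors but was graded 3 would therefore be unacceptable by the plan's own list, yet would count as zero under both the 15% and the 33% rule.

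At stake is the preset part of the safety monitoring: a count that suspends accrual without anyone having to judge that it should. Followed as written, it could miss part of a toxicity class that the plan singles out.

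**Working it through.** **1. Do the printed boundaries match the 15% rule?** The inputs, all from 9.4.9, are a 15% limit, a one-sided 90% lower confidence limit, and the pairs 2/3, 3/7, 4/12, 5/17 and 6/20. The exact (Clopper-Pearson) lower limit for r events in n subjects is the 10th percentile of a Beta(r, n − r + 1) distribution.

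| Pair | Lower limit | Same count, one more subject |
|---|---|---|
| 2/3 | 19.6% | 14.3% |
| 3/7 | 17.0% | 14.7% |
| 4/12 | 15.4% | 14.2% |
| 5/17 | 15.1% | 14.2% |
| 6/20 | 16.6% | not needed (accrual capped at 20, Section 9.3.2) |

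Every pair exceeds 15%, and each of the first four is the last sample size that does. The boundaries are correct for whatever event is counted. The question is only which event that should be.

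**2. What would a vasopressor-treated Grade 3 DLT contribute?** To the 15% rule, nothing, because it is not Grade 4. To the 33% rule, nothing, for the same reason. To the ventilatory trigger, nothing, unless the patient was also ventilated.

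**3. Can such an event occur?** The documents do not reproduce CTCAE v3.0 and do not say that vasopressor use is Grade 4 by definition. Three places point towards lower-graded events.

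- Section 10.2.3.2.2 introduces vasopressors with "Symptomatic hypotension that does not respond to these measures requires". The bullets under that step include a cross-reference for Grade 3 hypotension and none for Grade 4.
- The same step permits re-dosing at 50% the next day once vasopressors are no longer needed. Section 5.4.4.1 gives no further treatment in the course after related Grade 4 toxicity, with transient lymphopenia excepted.
- Section 1.3.5 reports two Phase I subjects with Grade 3 hypotension, one of whom is said not to have needed pressors, and no Grade 4 toxicity.

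**4. How much could it change the chance of suspension?** The vasopressor rate and the share graded below 4 are assumptions; the documents give neither. Subjects are taken as independent and the boundary is checked after each one up to 20. With full counting, the counted rate equals the vasopressor rate. As written, it is the vasopressor rate times the share graded 4. At a 10% rate with a quarter below Grade 4, for example, it is 0.10 × 0.75 = 7.5%. Exact sequential binomial probabilities of suspension are:

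| Assumed vasopressor rate | Full counting | As written, ¼ below Grade 4 | As written, ½ below Grade 4 |
|---|---|---|---|
| 5% | 1.1% | 0.6% | 0.2% |
| 10% | 6.4% | 3.1% | 1.1% |
| 13.9% | 15.0% | 7.2% | 2.5% |
| 15% | 18.1% | 8.7% | 3.1% |

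With none below Grade 4 there is no difference.

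**5. Which rates are plausible at 6 mg/m²?** Table 2 in Section 1.3.5 shows Grade 3 hypotension in 0 of 6 subjects at this dose in course 1, and the Overview reports no protocol-defined DLT in 14 Phase II subjects. Pooled informally as 0/20, the one-sided 95% upper bound is 1 − 0.05^(1/20) = 13.9%. Rates above about 14% therefore have little support.

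**The case against.** The strongest reply is that the gap may be empty. If CTCAE v3.0 puts every vasopressor-treated event at Grade 4, the two examples in item 1 cover the class and the counts do what the list says. The authors may have meant exactly that. The documents cannot exclude it.

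A reader might infer from Phase I, or from the hypotension guidance, that lower-graded vasopressor events have been shown to occur. The documents do not support that.

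- Pressor use in the second Phase I subject is inferred from a remark about the other. Both subjects received 7.5 mg/m², and the criteria version for those events is not stated.
- The Grade 3 bullet may be a general cross-reference; the vascular leak paragraph (10.2.3.3) ends with a similar one and has no vasopressor step.
- Next-day restart may only reflect that Sections 5 and 10 disagree, as they also do on neurotoxicity and Grade 4 fatigue.

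It is also fair to say that such an event would not go unseen. Treatment stops for any DLT, and resuming requires contact with the FDA (10.1.1). Working-group meetings discuss each subject, and the DSMC receives summaries twice a year (13.2). Keeping automatic counts for Grade 4 events is a defensible tiering in a 20-subject pilot.

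What remains is the internal mismatch. These safeguards work case by case or by judgment, and none is a count that suspends accrual. Expedited reporting is an uncertain backstop: 14.3.6 exempts Grade 3 hypotension that resolves within 48 hours of the last infusion of a course, while 14.2 requires reports of Grade 3 to 5 events that prolong hospitalization.

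**Conclusion.** The point holds as a mismatch between the events that 9.4.9 calls unacceptable and the events that it counts. A vasopressor-treated DLT graded 3 enters no suspension count.

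Its practical effect is conditional and modest. It is nil if all such events are graded 4. At an assumed 10% vasopressor rate with a quarter to a half graded below 4, the rule as written suspends accrual with probability 3.1% to 1.1%, where full counting gives 6.4%. At the 13.9% upper bound the figures are 7.2% to 2.5%, against 15.0%. These rest on assumed rates and grade splits, independent subjects, and an informal pooling of two small series.

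A reader might go further and conclude that the stopping boundaries are wrong, or that the trial lacks oversight of vasopressor events. Neither follows: the boundaries reproduce exactly, and the case-by-case safeguards are real. This is a low-severity fix.

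**What to change.** Add one sentence to 9.4.9:

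*For the 15% rule, any DLT (as defined in Section 5.4, so outside the surgical period) that requires vasopressors for hypotension or vascular leak counts as a Grade 4 hypotension event whatever its CTCAE grade; epinephrine given only for an allergic or infusional reaction does not count.*

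The DLT and surgical-period limits keep the count within the plan's own definition. The epinephrine clause is needed because 10.2.11 and 10.3.3.5 allow it for reactions of a different kind.

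Keep the boundaries 2/3, 3/7, 4/12, 5/17 and 6/20. They need no recalculation if 15% is kept, but the sponsor should confirm that 15% suits the wider event, since the limit is stated for Grade 4 events.

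The cost is a short amendment, that clinical confirmation, and a somewhat higher chance of a temporary suspension. With half of vasopressor events below Grade 4, the chance rises from 0.2% to 1.1% at a 5% rate and from 1.1% to 6.4% at a 10% rate. If the sponsor already regards all vasopressor use as Grade 4, the sentence changes nothing except to make that explicit.
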